14. PRIVACY AND CONFIDENTIALITY OF SUBJECTS AND RESEARCH DATA

Assessment data is stored in REDCap, a software toolset and workflow methodology for the electronic collection and management of research and clinical trial data. REDCap was created specifically around HIPAA-Security guidelines, including a complete audit trail, user- and individual form-based privilege options, and integration with institutional servers. The REDCap database is password protected, and access is limited to relevant study personnel. All research data are coded using a study identification number. Identifying information and protected health information is marked with REDCap's "identifier" designation, which allows it to be

automatically removed in data exports. Additionally, access to any forms containing identifying or protected health information is only granted to those investigators, clinicians, or staff who need to know this information for the study. All identifying data not in REDCap is stored in password-encrypted files. Access to these files is limited to investigators and support personnel with the need to enter or analyze data.

Text messages are sent from a study-issued phone purchased by URMC. The texts sent by study staff do not contain PHI. Content of the texts may include a reminder for a follow-up assessment phone call, a REDCap survey link if subjects cannot be reached by phone for a follow-up assessment, or an Amazon gift code for compensation after a follow-up assessment has been completed. Subjects receive texts only if they are willing and able to receive them. Acceptance of text is not a condition of participation in the study. Subjects may decline to receive texts during consent and opt out by sending a STOP reply to any text. Alternatively, emails, letters, and/or calls are used to maintain contact during follow-up. Study staff document the preferred method of contact for each subject and update their preference if it changes over the course of the study.

All research and clinical information obtained is kept confidential unless the subject is at risk for danger to themselves or others as determined by the research team based on available information. Subject well-being is carefully monitored throughout the study. If the clinical information obtained in the course of research assessments pertains to subject safety (e.g., intent to harm oneself or others), then confidentiality will not be maintained, and appropriate treating professionals will be informed. As required to promote subject safety, this clinical information may be provided to other clinicians (or family members) to facilitate appropriate treatment and minimize the risks of self-harm or harm to others. This information may include the subject's medical history, financial and social resources, and history of suicidal behavior if known.

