3. Proportion of patients who answered "no" for both questions 1 ("Have you wished you were dead or wished you could go to sleep and not wake up?") and 2 ("Have you actually had any thoughts of killing yourself?") of the C-SSRS (time frame: day 14 [+ 7 days], day 30 [+ 7 days], and day 60 [+ 10 days] from the first RS-tDCS session). This will help to determine the proportion of subjects who presented suicidal ideation relapse since the negative answer for both questions will be an inclusion criterion for this study.

4. Intensity of rumination as assessed by the Ruminative Responses Scale (RRS) (44) (time frame: day 14 [+ 7 days], day 30 [+ 7 days], and day 60 [+ 10 days] from the first RS-tDCS session):

The RRS encompasses 22 items. Each item is rated on a 4-point Likert scale: 1, almost never; 2, sometimes; 3, often; 4, almost always. The score on this scale is obtained by simply summing the scores on the 22 items.

5. Symptoms associated with suicidal ideation as assessed by the Concise Associated Symptoms

Tracking (CAST) scale (time frame: day 14 [+ 7 days], day 30 [+ 7 days], and day 60 [+ 10 days] from the first RS-tDCS session):

The 16 items of the CAST Scale assess symptoms across five domains: anxiety (three items, subscore range 3-15), irritability (five items, subscore range 5-25), mania (four items, subscore range 4-20), insomnia (two items, subscore range 2-10), and panic (two items, subscore range 2-10). The total CAST score ranges from 16 to 80. Each item is rated on a 5-point Likert scale: 1, strongly disagree; 2, disagree; 3, neither agree nor disagree; 4, agree; or 5, strongly agree, with higher scores indicating more severe symptoms.

6. Depressive symptoms as assessed by the Montgomery-Asberg Depression Rating Scale (MADRS) (time frame: day 14 [+ 7 days], day 30 [+ 7 days], and day 60 [+ 10 days] from the first RS-tDCS session):

MADRS is a 10-item questionnaire that includes questions on the following symptoms: 1. Apparent sadness 2. Reported sadness 3. Inner tension 4. Reduced sleep 5. Reduced appetite 6. Concentration difficulties 7. Lassitude 8. Inability to feel 9. Pessimistic thoughts 10. Suicidal thoughts. Each item yields a score of 0 to 6. The overall score ranges from 0 to 60. A higher MADRS score indicates more severe depression. The usual cutoff points are:

0 to 6 - normal/symptom absent; 7 to 19 - mild depression; 20 to 34 - moderate depression; >34 - severe depression.

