8. STUDY PROCEDURES

The pre-screening will be carried out through the electronic hospital medical record to identify potential subjects. Once the potential subject is identified, research staff will visit the unit where the patient is receiving treatment (inpatient unit or CPEP) and talk with unit staff in person, providing information about the study. Then, the research staff will ask unit staff to determine the most appropriate time for the research staff to meet with the patient based on knowledge of patient status and needs.

[figure not shown]
After screening and signing consent, the research study staff will collect demographic and general medical history data, apply the clinical questionnaires, and conduct the orientation tDCS session as part of the in-person baseline assessment (Table 1 and Figure 3). This demographic, general medical history, and clinical data will be collected and stored in the REDCap through a tablet or another portable electronic device. Per subject need/request, research study staff reads aloud instructions and questions while subjects hold the tablet to record their answers. If the REDCap site is down or malfunctioning, screening, consent, and questionnaires are completed on paper and later entered into REDCap.

The orientation session includes presenting the Soterix Medical mini-CT device to the subject to show how to turn it on/off, how to insert the device unlock codes for one-time use, how to correctly adjust the SNAPstrap headgear, and answer any questions they may have. As part of the orientation session, research staff will also conduct a 90-s tolerability test, with 2.0 mA as the starting point (electrical current intensity of the study protocol). During this test, the current intensity is ramped up to 2.0 mA and the subject will receive the stimulation for 90 seconds. The tolerability will be determined by subject rating below 7 on the 0-10 Visual Analogue Scale (VAS) of pain. If the subject finds the target tDCS dose intolerable (i.e., VAS 7 or higher), subjects will have the option of another test, with the amperage dose decreased by 0.5 mA (i.e., to 1.5 mA). If this lower amperage is also intolerable, the subject will be excluded from the study (39, 46). Thus, the orientation session aims to 1) familiarize the subject with the

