device, how to turn it on/off, and insert the unlock codes for one-time use; 2) to assess if the subject tolerates the protocol electric current through the tolerability test; 3) answer any questions the subjects may have. As the Soterix Medical mini-CT device will be with the subjects during the RS-tDCS sessions, subjects will be asked to sign an IRB-approved device loan agreement at the baseline.

Clinical questionnaires will be re-administered at day 14 [+ 7 days], day 30 [+ 7 days], and day 60 [+ 10 days] from the first RS-tDCS session session15 (Figure 3). While we aim to reach subjects on the phone for follow-up, research staff may email or text subjects to schedule the RS-tDCS sessions and clinical assessments. Subject identifying information and protected health information (PHI) is not exchanged in the text messages themselves. Detailed information about text messaging is included under the "Privacy and Confidentiality of Subjects and Research Data" section. Security risks associated with text messaging are described in detail during consent.

After baseline assessment, research staff not involved in the RS-tDCS supervisions and clinical assessments will randomize the subject to active or sham control group and set up the device condition (active or sham), program the intensity for the active condition (either 2.0 mA or 1.5 mA, according to the tolerability test) and duration (30 minutes) of each session, and get the device unlock codes for one-time use to be provided by the research staff to the subject immediately before each session. The discharge day will be tracked daily by the research staff through the electronic hospital medical record. Once the subject is discharged, research staff will deliver the RS-tDCS device by mail to the subject's address in a pre-paid FedEx package to send it back and contact the subject once the device has arrived at their home (by using the mail tracking number) to schedule the first RS-tDCS session.

*device set up for the condition (active or sham), and locked (unlock codes for one-time use will be provided before each session); **day 1 being the first RS-tDCS session and no sessions on weekends. CPEP: Comprehensive Psychiatric Emergency Program; DLPFC: dorsolateral prefrontal cortex; RS-tDCS: remotely supervised transcranial direct current stimulation.

RS-tDCS sessions:

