The tolerability and safety of home-based tDCS were assessed over 6,779 sessions from six clinical trials, with daily session, varying from 10 to 60 applications. The authors reported no serious adverse events, a similar proportion of tingling (68%), itching (41%), and warmth sensation (42%) between active and sham groups, and no participant discontinuation due to lack of tolerability (39). As described in "Study procedures," a tolerability test will be performed as part of the orientation session to verify if the subject can tolerate the electric current established in the protocol. Subjects will be informed that they can stop an RS-tDCS session anytime. During the RS-tDCS session, the stimulation will be stopped if the subject reports a sensation of pain rated as an intensity of 7 or above on a 1-10 scale (46). If the subject reports any event of critical concern related since the last RS-tDCS session, the next RS-tDCS session will not start until clear that the event is not stimulation-related. All devices function only after the inclusion of a unlock code for one-time use. The unlock codes for one-time use allow the device to function only once a day, just after the inclusion of the code, with the level of electric current and duration of the session determined by the protocol, both (electric current level and duration of the session) pre-programmed on the device before it is delivered to the subject.

Imminent risk of suicide, for the purposes of this study, refers to a subject who is currently 1) thinking about suicide; 2) preparing for suicide and/or having planned for suicide; and has 3) some intent to act on the suicide plan within the very near future (generally 48 hours).

This may differ for each case and therefore, clinical judgment along with timely consultation are needed for determination of imminence. Thus, to assess imminent risk of suicide, the following procedures will be undertaken:

a) at the baseline assessment in the hospital:

- after the C-SSRS assessment, research staff will ask the subject if there is current active suicidal ideation with plan and intent. If the subject reports current active suicidal ideation plan and intent at the baseline, research staff will inform the subject that they need to communicate this information (about the active suicidal ideation with specific plan and intent) to the unit staff in charge of the patient due to safety concerns.

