- research staff will also communicate with the unit staff in case of any concerns about the subject during the baseline assessment.
- For this assessment, the following questions will be added, and the research staff must provide the answers ("yes" or "no"): "Active ideation with plan and intent *currently*?"; "Are you otherwise concerned about the patient at all?"

b) at the RS-tDCS sessions:

- after the C-SSRS screening version assessment, research staff will ask the subject if there is current active suicidal ideation with plan and intent. If the subject reports current active suicidal ideation plan and intent, research staff will inform the subject that they need to communicate this information (about the active suicidal ideation with specific plan and intent) to a licensed clinician from the research team to discuss the need for a specialized assessment.
- research staff will also communicate the licensed clinician in case of any concerns about the subject during the RS-tDCS sessions.
- For this assessment, the following questions will be added, and the research staff must provide the answers ("yes" or "no"): "Active ideation with plan and intent *currently*?"; "Are you otherwise concerned about the patient at all?"

c) at the clinical assessments (day 14, day 30, and day 60 from the first RS-tDCS session):

- after the C-SSRS assessment, research staff will ask the subject if there is current active suicidal ideation with plan and intent. If the subject reports current active suicidal ideation plan and intent, research staff will inform the subject that they need to communicate this information (about the active suicidal ideation with specific plan and intent) to a licensed clinician from the research team to discuss the need for a specialized assessment.
- research staff will also communicate the licensed clinician in case of any concerns about the subject during the follow-up assessments.
- For this assessment, the following questions will be added, and the research staff must provide the answers ("yes" or "no"): "Active ideation with plan and intent currently?"; "Are you otherwise concerned about the patient at all?"

The licensed clinician will follow the best policies and procedures of URMC and applicable state law for providing resources and determining if emergency evaluation is required. At minimum, the licensed clinician will:

- Advise the subject about emergency contact number

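### The texted survey-link fallback at follow-up gives no way to perform the staff risk step required after the C-SSRS, and neither phone nor link lets a rater see MADRS apparent sadness

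*Combined protocol and SAP*

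**What the plan says.** Table 1 (section 4) schedules the C-SSRS, RRS, CAST and MADRS at days 14, 30 and 60, all under the remote column. Section 8 gives the telephone as the intended route ("While we aim to reach subjects on the phone for follow-up") and sends the reader to section 14 for the details of texting. Section 14 lists what a text may contain. One entry is "a REDCap survey link if subjects cannot be reached by phone for a follow-up assessment". Reminders of a follow-up call are a separate entry in the same list, so the link is a way of doing the assessment and not of scheduling it. No scale is named as included or excluded.

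Section 9, part c, governs the same three visits: "after the C-SSRS assessment, research staff will ask the subject if there is current active suicidal ideation with plan and intent". Two yes/no items are then added, one on current ideation with plan and intent and one on whether there is any other concern about the patient. For these, "the research staff must provide the answers". The same section says that "clinical judgment along with timely consultation are needed for determination of imminence". Part c makes no exception for any mode of contact.

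On measurement, secondary outcome 6 in section 4 calls the MADRS a questionnaire and begins its item list with "1. Apparent sadness 2. Reported sadness 3. Inner tension". Each item scores 0 to 6, for a total of 0 to 60. Section 17 compares the arms at each time point by t-test or chi-square test and does not mention mode of collection.

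**The concern.** Two parts of the protocol apply to the same visit and cannot both be carried out as written. If a subject completes the C-SSRS through a link, no staff member is present to ask the next question or to form the judgement that the second added item calls for. The fallback applies to subjects whom the telephone has failed to reach, in a population that section 9 describes as likely to be at increased risk.

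Timing adds to this. The C-SSRS screening version is given after each stimulation session and ends when the sessions end. For a subject who completes ten weekday sessions on schedule, the day 30 and day 60 assessments are the only scheduled risk checks left.

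There is also a smaller measurement question. Baseline is in person and follow-up is by phone or link, and the MADRS keeps apparent sadness apart from reported sadness. A rater who cannot see the subject has no direct basis for the first. Results from different modes would be pooled with no record of which was used.

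**Working it through.** The plan states no figure on this point, so there is none to reproduce. The check is mainly a comparison of texts.

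**1. Can the section 9 step be done through the section 14 link?**
- Required in section 9, part c: a question put by staff after the C-SSRS; two items answered by staff; referral to a licensed clinician on a positive answer or a concern.
- Available through a link completed alone: the subject's own entries only.
- The first two requirements need a staff member in contact with the subject. The third needs someone to read the entries, and no section says who does so, how soon, whether an answer raises an alert, or whether live contact must follow.

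**2. Do other sections fill the gap?**
- Section 5 requires permission to contact at least one other person and limits entry to the area served by the Mobile Crisis Team. Neither is tied to survey answers.
- Sections 14 and 16 say that treating professionals will be informed if information bearing on safety is obtained. They set no review step and no timing.

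**3. How many assessments could be affected?**
Inputs from the documents: 20 subjects (section 17) and 3 follow-up visits (Table 1), so 20 x 3 = 60 scheduled follow-ups. The share done by link, q, is not given and is assumed. Expected number = 60q:
- q = 5%: 3
- q = 10%: 6
- q = 20%: 12
- q = 30%: 18

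These count as affected only if the link carries the C-SSRS, which section 14 neither says nor rules out.

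**4. Weight of the MADRS item.** 6 / 60 = 10% of the maximum total. It applies to phone as well as link.

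**5. Would mode bias the comparison of arms?** Let f be the share of an arm using the link and b the score shift caused by that mode. With the same b in both arms, the bias in the mean difference is b x (f_active - f_sham). With 1:1 allocation of 20, take 10 per arm. For the C-SSRS intensity score (0 to 25), with b assumed between 1 and 5 points:
- 1 active and 1 sham link user: b x (0.1 - 0.1) = 0
- 1 active and 3 sham: b x (0.1 - 0.3), a shift of 0.2 to 1.0 points in size
- 1 active and 5 sham: b x (0.1 - 0.5), a shift of 0.4 to 2.0 points in size

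Both b and the split are assumptions. Equal use with an equal mode effect gives no bias at all. If b differs between arms, the bias is b_active x f_active - b_sham x f_sham, which need not vanish even when use is equal. The documents give no basis for choosing among these cases.

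**The case against.** The strongest reply is that the conflict is read from silence. Section 14 is about privacy and lists possible contents of a text. It does not say that the C-SSRS is on the link or that the link ends staff contact, and section 9 could be read as still binding whatever the mode. This stands in part. A reader might infer that every link-completed C-SSRS omits the risk step, or that a positive answer will lie unread; the documents establish neither, because later contact is neither required nor excluded. What remains is that staff following both sections have no stated way to perform the step.

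A reader might also infer that the link replaces observer rating with self-report across the C-SSRS and MADRS. The documents do not support that. No section names the rater. At the in-person baseline, if the subject needs or asks for it, "research study staff reads aloud instructions and questions while subjects hold the tablet to record their answers", so baseline answers may already be recorded by the subject. The observer argument is firm only for apparent sadness, by its name, and for the staff-answered risk items.

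Third, it is tempting to say that link users form an outcome-related subset and that the arm comparison is biased. The first is plausible but not stated anywhere. The second needs unequal use or unequal mode effects. Nor does a difference in footing between baseline and follow-up enter the stated analysis, since section 17 specifies no change from baseline and a shift common to both arms cancels.

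Finally, removing an instrument from the link could turn a response into no response for the least reachable subjects. That cost is real and is a reason to leave the choice of clinical procedure to the sponsor.

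**Conclusion.** The point holds in a limited form. Section 14 permits a survey-link follow-up with no limit on its content, and section 9 requires a staff-asked and staff-answered step after the C-SSRS that an unattended survey gives no means to perform. The general safeguards in sections 5, 14 and 16 do not supply the missing link, so the passages must be reconciled. The number of assessments involved is unknown; 3 to 18 of 60 corresponds to assumed link use of 5% to 30%.

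Separately, one MADRS item worth up to 10% of the total cannot be rated by sight over phone or link. How far this matters depends on who the rater is, which the documents do not say. No between-arm bias is shown, and the primary feasibility outcome, completed sessions, is untouched.

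**What to change.** Reconcile section 14 with section 9, part c. State which instruments the survey link may carry, and how the required staff risk step is met whenever the link is used. The clinical procedure itself is for the sponsor to decide.

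For measurement:
- Make the videoconference already used for the stimulation sessions the default for the MADRS, with phone as back-up. Internet access is already an entry criterion.
- Record the mode of collection at each follow-up visit.
- Flag MADRS totals obtained without sight of the subject, so that they can be described by arm.

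The cost is protocol wording and one REDCap field. The downside is that a few scores may be missing where they would otherwise have been completed by link, which counts for something with about 10 subjects per arm.

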15. DATA / SAMPLE STORAGE FOR FUTURE USE

We are willing to share data with other researchers and have chosen measures that are useful for future analyses; however, the data sharing agreement involves sharing only de-identified data with other investigators and the use of data-sharing agreements that provide for: (1) a commitment to use the data only for research purposes and not to identify any individual subject; (2) a commitment to secure the data using appropriate computer technology; and (3) a commitment to destroy or return the data after analyses are completed.

